4. INCLUSION/EXCLUSION CRITERIA

DDM Inclusion and Exclusion Criteria					
Inclusion Criteria	Exclusion Criteria				
-Age 50 years or older -English speaking -Admitted to the intensive care unit (medical or surgical) -Expected mechanical ventilator support for ≥48 hours -Consentable through a legally authorized representative -Have access to a telephone	-History of dementing illnesses and other neurodegenerative diseases such as Alzheimer's disease or vascular dementia -Psychiatric illness which is not well controlled -Alcohol withdrawal symptoms/concern for withdrawal -Suspected or confirmed drug intoxication/overdose -Traumatic brain injury, ischemic or hemorrhagic cerebrovascular accident, or undergoing neurosurgery -Uncorrected hearing or vision impairment including legal blindness -Incarcerated at the time of study enrollment -Enrolled in another clinical trial which does not permit co-enrollment				
	-Any medical condition precluding safe use of headphones such as: skin breakdown, burns, facial or skull fractures				

5. ENROLLMENT and RANDOMIZATION

Clinical Settings and Study Population: Patients will be recruited from two Indianapolis Hospital systems: Eskenazi Health and Indiana University Health. Patients will also be recruited from Mayo Clinic Rochester.

Recruitment Targets: Final study sample will comprise 160 mechanically ventilated older adults ≥50 years of age.

Screening and Enrollment: Research staff will review the electronic medical records of ICU patients daily for eligibility. Eligible patients' clinical teams will be approached if necessary to confirm eligibility. Eligible individuals (those who meet inclusion criteria and do not meet any exclusion criteria) will be screened up to twice per day for delirium until approached for the study using the CAM-ICU-7. Once eligibility is confirmed, the research team will approach patients or their legally authorized representatives for consent depending on patients' clinical status. Patients consented through their legally authorized representative will be reconsented once clinically able.

Randomization: Using a computer-generated list of random numbers created by study statistician, participants will be randomized by permuted block with varying block sizes. Randomization will occur after consent in a 1:1 manner and will be stratified based on hospital location.

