Clinical data (lab values)	EMR	X	Daily			
Comorbidities (Charlson) ^a	EMR	X				
Baseline cognitive function (IQCODE) ^b	Caregiver interview	x				
History of depression, anxiety	EMR	X				
Diagnoses	EMR	X			X	
Severity of Illness ^c (APACHE II, SOFA)	EMR	X (APACHE)	Daily (SOFA)			
Functional Status ^d (ADL, IADL)	EMR	X				
Medications ^c (sedatives, analgesics, anxiolytics, antipsychotics)	EMR, patient, caregiver	X	Daily	Daily	X	X
Duration of Mechanical Ventilation, Length of ICU and Hospital Stay	EMR				х	
Mortality	EMR				X	X
Discharge Disposition	EMR				X	
ABCDEF bundle adherence	EMR, Nursing reports	х	Daily	Daily		
Intervention characteristics	iPad App and Web Portal	X	х			
Physiologic Parameters (respiratory rate, heart rate, blood pressure)	EMR	х	4XDaily	Daily		
Delirium, Pain, Anxiety ^f (RASS, CAM-ICU, CAM-ICU- 7, CPOT, VAS-A)	Direct Assessment		2XDaily (CAM-ICU, CAM-ICU-7) 4XDaily (RASS, CPOT, VAS-A)	2XDaily		
Cognition (IUTBANS) ^g	Direct Assessment					X
Mood symptoms ^h (GAD-7, PHQ-9) Healthcare Utilization	Direct Assessment					X

^aChronic comorbidities measured through Charlson Comorbidity Index⁸⁹, ^bIQCODE: Informant Questionnaire on Cognitive Decline in Elderly⁹⁰, ^cSeverity of Illness measured through APACHE II⁹¹ and SOFA⁹², ^cFunctional Status measured through Katz and Lawton Scales^{33,94}, ^cAnlgesic and sedative exposure is defined as aggregate measure of pain and sedation intensity and the drug frequency in a 24 hour period. We will aggregate dose frequency and dosing intensity by each enrollment day. A dose frequency analysis will be used⁹⁵⁻⁹⁷, ^cBASS; Richmond-Agitation Sealation Scale⁷⁶, CAM-ICU: Confusion Assessment Method in the ICU⁹⁷, CPOT: Critical Care Pain Observation Tool⁷⁸, VAS-4: Visual Analog Scale-Anxiety^{31,8} IUTBANS: Indiana University Telephone-Based Assessment of Neuropsychological Status⁸⁴; ^bPHQ-9: Patient Health Questionnaire⁸⁵, GAD-7, Generalized Anxiety Disorder Scale⁸⁷; ^c Captured through Indiana Network for Patient Care (INPC)

reliability as well as construct, criterion, procedural and factorial validity for the diagnosis of major depression and general anxiety disorder.⁸⁵⁻⁸⁸ Research staff will collect PHQ-9 and GAD-7 over the phone at 3 months post-hospital discharge.

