3. STATISTICAL CONSIDERATIONS

Statistical Analyses: We will compare baseline patients' demographic characteristics (age, gender, race and levels of education) between the intervention and control group using two sample t-tests for continuous variables and Chi-square tests for categorical variables to determine whether the two groups are balanced in these variables. Variables that are found to be unbalanced will be included as covariates in all models comparing outcomes between the two groups. Intention to treat approach will be used in all analyses.

a. Primary Specific Aim: Delirium/coma free days by day 7 will be compared using analysis of covariance (ANCOVA) model with group (intervention versus control) as the independent variable while adjusting for the baseline patients' demographic variables not balanced between the two groups. For patients discharged before day 7, the days from discharge to day 7 will be counted as delirium/coma free. For patients who died before day 7, 0 delirium/coma free days will be counted from date of death to day 7. We have used the same approach in our previous trials and this approach is able to appropriately handle potential missing data due to discharge or death of patients before day 7.¹⁷

Secondary Specific Aim 1: Mixed effects models will be used to compare delirium severity (CAM-ICU-7), pain (CPOT) and anxiety scores (VAS-A) measured twice daily from randomization to day 7, time of death or discharge. In each of the models, repeated CAM-ICU-7, CPOT or VAS-A scores will be the outcome variable respectively. Group, time, group and time interactions will be included as independent variables while adjusting for potential baseline covariates. Significant group and time interactions will indicate differences in changes of these outcomes between the two groups. Post-hoc analyses will be conducted to determine the earliest times when significant differences between these outcomes can be detected. We will compare various variance covariance structures including autoregressive (AR) and variance components blocked by time of the day (am versus pm) using the likelihood ratio tests to determine the most appropriate covariance structure. We will also examine potential non-linear trajectories of change in these outcomes by including quadratic time in the models and by fitting spline models.

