- **b. Secondary Specific Aim 2:** ANCOVA models will be used to compare IU-TBANS, PHQ-9, and GAD-7 collected at three months post hospital discharge with group as the independent variable while adjusting for potential baseline covariates.
- **c. Missing Data:** We expect up to 20% of patients who may not complete the primary outcome at day 7 due to death in the ICU or discharge before day 7. We will conduct sensitivity analyses with varying assumptions for the patients with missing outcomes to determine the robustness of our findings. The mixed effects model we propose for Secondary Aim 1 is robust to the missing at random assumption and is unbiased if we include all relevant covariates in the model. We will also compare baseline characteristics of patients with 3-month

assessment and those who are lost to follow-up and adjust for the variables associated with missing data to ensure unbiased estimation and inference.

d. Sex as a Biological Variable: Both male and female patients will be included in the trial. We do not anticipate treatment efficacy will differ by sex. We will include sex as a covariate in each analysis to

determine whether estimated treatment effects differ by sex.

e.Sample Size and Power: Sample size estimation is based on the observed effect size from our pilot data where the intervention group had higher delirium/coma free days from the control group with estimated effect size of 0.52. Using two sample t-test, we estimate that we will need 128 total patients with complete data to detect an effect size of 0.5SD or higher at α =0.05. For robustness of results, we also estimated power if we assume Poisson distribution for mean delirium/coma free days with a total 128 patients observed at day 7, we will have 98.7% power to detect group difference at α =0.05 using the nonparametric Wilcoxon test. Allowing up to 20% attrition rate for patients dropping out before day 7, we will enroll 160 total patients for this trial (80 per group).

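### The IQCODE, the schedule's only direct measure of pre-illness cognition, is collected at enrollment but named as a covariate in no analysis, so adjusting the 3-month cognition comparison for it is left to chance or analyst choice

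*Combined protocol and SAP*

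**What the plan says.** **The analysis.** In Statistical Considerations, item b (Secondary Specific Aim 2), "ANCOVA models will be used to compare IU-TBANS, PHQ-9, and GAD-7 collected at three months post hospital discharge". Group is the independent variable, and the sentence ends by adjusting for potential baseline covariates, none of which is listed.

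**The measure.** The data-collection table in Study Procedures has a row beginning "Baseline cognitive function (IQCODE", obtained by caregiver interview at enrollment. The revised table in the 5/22/2023 amendment keeps it. No statistical section mentions it.

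**The covariate rules.** There are four:
- *Opening paragraph of Statistical Considerations, for all models:* "We will compare baseline patients' demographic characteristics (age, gender, race and levels of education) between the intervention and control group", and then "Variables that are found to be unbalanced will be included as covariates in all models comparing outcomes between the two groups". The IQCODE is not on that list.
- *Item c (Missing Data):* patients with and without the 3-month assessment are compared at baseline, and variables associated with missingness are adjusted for.
- *Item d:* sex is a covariate in each analysis.
- *Amendment, Exploratory Aim 1:* the longitudinal IU-TBANS model adjusts for stratification variables and for baseline covariates that differ significantly in univariate comparisons.

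**Power.** Item e and the paragraph after it give 80% power for 0.5 SD by two-sample t-test for the 3-month outcomes (called Aim 3 there), without a sample size.

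**The concern.** Secondary Specific Aim 2 rests on a cognitive score taken once, 3 months after discharge. IU-TBANS cannot be given before the critical illness. The extra IU-TBANS added in 2023 is taken around hospital discharge, after randomization and treatment. Treatment may have affected it, so it cannot stand in for pre-illness cognition. The IQCODE can.

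A baseline variable earns its place in an ANCOVA by its correlation with the outcome, not by whether the arms happen to differ on it. A balance test is therefore a poor way to choose covariates, and the list it works from here omits the one variable aimed directly at prior cognition. An unnamed covariate set also leaves the model open to choice once the data are seen.

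At stake are precision on a secondary outcome, and an estimate that moves with whatever imbalance in pre-illness cognition the randomization produced.

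**Working it through.** **1. Can the IQCODE enter the 3-month model?**

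| Route | Applies to 3-month IU-TBANS? | Does the IQCODE enter? |
|---|---|---|
| Balance test, all models | Yes | Not among the four variables tested |
| Item b, unnamed covariates | Yes | Only if the analyst chooses it |
| Item c, missingness | Yes | Only if it proves associated with loss to follow-up |
| Item d, sex | Yes | Not relevant |
| Amendment, univariate differences | No (Exploratory Aim 1) | Only if the arms differ significantly |

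Entry is possible but never assured.

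**2. Reproduce the plan's power.** Inputs: 0.5 SD and α = 0.05 (plan). The 3-month sentence gives no sample size. I assume the 128 complete patients of the primary calculation, which at 1:1 is 64 per arm.

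Noncentrality = 0.5 × √(64/2) = 2.83, with 126 degrees of freedom. Two-sided power from the noncentral t is **80.1%**, so the stated 80% reproduces. It is an unadjusted figure.

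**3. Add the IQCODE as a fixed covariate.** The documents give no correlation between IQCODE and IU-TBANS. I assume r (absolute value) from 0.2 to 0.5. The residual variance factor is 1 − r², and the effect in residual SD units is 0.5/√(1 − r²). The same power calculation then gives:

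| r | 1 − r² | 0.5/√(1 − r²) | Power, 64 per arm |
|---|---|---|---|
| none | 1.00 | 0.500 | 80.1% |
| 0.2 | 0.96 | 0.510 | 81.7% |
| 0.3 | 0.91 | 0.524 | 83.7% |
| 0.4 | 0.84 | 0.546 | 86.5% |
| 0.5 | 0.75 | 0.577 | 90.0% |

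The comparison is with a model that has no covariates at all.

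**4. Chance imbalance.** The standard error of the between-arm difference in mean IQCODE, in SD units, is √(2/64) = 0.177. The 95% range is ±1.96 × 0.177 = ±0.35 SD. An imbalance at that limit shifts the unadjusted IU-TBANS difference by r × 0.35:
- r = 0.2: 0.07 SD
- r = 0.3: 0.10 SD
- r = 0.4: 0.14 SD
- r = 0.5: 0.17 SD

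The target effect is 0.5 SD. At one standard error the shifts are about half as large (0.035 SD at r = 0.2, 0.088 SD at r = 0.5).

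Steps 3 and 4 describe one loss, not two. The variance of this shift is r² × 2/64, which is the fraction r² of the unadjusted variance that adjustment removes.

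**5. Fewer patients at 3 months.** The 20% allowance in item e covers dropout before day 7, and none is stated for later loss. If 96 patients were assessed (48 per arm, an assumption), unadjusted power would be 67.9%, rising to 72.0% at r = 0.3 and 79.9% at r = 0.5.

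**The case against.** **The text does not exclude the IQCODE.** The sentence on the 3-month ANCOVA goes on to adjust for baseline covariates. The schedule labels the IQCODE as baseline cognitive function, which makes it a natural candidate, and item c gives a second route. This stands. A reader might infer that the IQCODE enters no model, or that the comparison has no adjustment for pre-illness cognition, but the documents do not say so. They leave the matter undecided.

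**Randomization protects the comparison.** Omitting a baseline covariate does not bias the comparison in expectation among randomized patients, and the unadjusted standard error already allows for chance imbalance. This also stands, so the point is about precision and prespecification.

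**The gain may be small.** By its name the IQCODE records informant-rated decline rather than level of cognition. Excluding known dementia narrows its range, so a low r is plausible, and at r = 0.2 the gain is 1.6 points of power (81.7 − 80.1). The plan already includes sex and any unbalanced demographics, and the IQCODE's contribution beyond those, or beyond age and education, is not estimated here. All of this limits the size. It does not argue for leaving the covariate undefined.

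**Eligibility.** A reader might infer that impaired patients are screened out by chart review alone, since the exclusion is "History of dementing illnesses and other neurodegenerative diseases such as Alzheimer's disease or vascular dementia". The enrollment section adds that "Eligible patients' clinical teams will be approached if necessary to confirm eligibility". That check is conditional and is not a cognitive test, but chart review is not the sole source. No change to eligibility follows from this point.

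**Conclusion.** The point holds as one of prespecification and efficiency. The IQCODE is collected before the intervention, is the only direct measure of pre-illness cognition in the schedule, and is assigned no analytic use. Whether the 3-month IU-TBANS comparison adjusts for it depends on an unnamed covariate set or on data-driven rules.

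With 64 per arm, a 0.5 SD effect and two-sided α = 0.05, fixing it in the model would raise power from 80.1% to between 81.7% (r = 0.2) and 90.0% (r = 0.5). The sample size and r are assumptions, and the reference is a model without covariates. A chance IQCODE imbalance at the edge of its 95% range would move the unadjusted difference by 0.07 to 0.17 SD over the same values of r.

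Two further readings are not supported. The stated 80% is not wrong: it reproduces. Nor is there a demonstrated gain for Exploratory Aim 1, which tests a group-by-time interaction. A main effect of IQCODE would do little for that term, and no benefit has been calculated.

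**What to change.** In Statistical Considerations, item b, replace the unnamed covariates for the 3-month IU-TBANS ANCOVA with a fixed set: IQCODE score, age and education, together with sex as already planned. State that these enter whatever the observed balance. State a simple baseline imputation for patients with no informant, and show the IQCODE by arm in the baseline table.

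The cost is a change of wording before the outcome data are analyzed. The IQCODE, age, sex and education are already collected, and eligibility and sample size do not change. The downsides are minor: some IQCODE values will be missing, and the gain will be small if r is low.

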Primary Specific Aim: Test the efficacy of music intervention in *improving delirium/coma free days* among mechanically ventilated patients as compared to attention control. Hypothesis: Patients in the music intervention group will have higher number of delirium/coma free days as measured by the Confusion Assessment Method for the ICU (CAM-ICU) at seven days post randomization.

Secondary Specific Aim 1: Test the efficacy of music intervention in *improving delirium severity, pain and anxiety* among mechanically ventilated patients as compared to attention control. Hypotheses: Patients in the music intervention group will have lower delirium severity, pain and anxiety scores as measured by the CAM- ICU-7, Critical Care Pain Observation Tool (CPOT) and Visual Analogue Scale-Anxiety (VAS-A) respectively at seven days post-randomization.

Secondary Specific Aim 2: Test the efficacy of music intervention in *improving the long-term neuro-psychological outcomes* as compared to attention control. Hypotheses: Patients in the music intervention group will have higher cognitive scores as assessed by the Indiana University Telephone Based Assessment of Neuropsychological Status (IU-TBANS), and lower depression and anxiety scores on the Patient Health Questionnaire (PHQ-9) and Generalized Anxiety Disorder (GAD-7) scales at 3 months post hospital discharge.

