- **6. Limits of Assumptions:** It is possible that baseline differences between the groups, excessive study dropouts and/or missing data by the interim measurement time point (midway point to targeted enrollment) will limit the value of data analysis. Baseline differences will be evaluated after the first measurement time point and effects on the power to detect differences in the primary outcome will be evaluated and communicated to the PI, safety officer, and NIA. Given the monitoring plans outlined elsewhere in this document, it is exceedingly unlikely that there will be baseline differences between groups of any magnitude to threaten the validity of the study.

Dropout rates higher than 15% would be of concern, so we propose to monitor the dropout rate quarterly. Alert points are set at dropout rates of 15% (low alert), 25% (mid-alert), 35% (high alert) and 45% (extreme alert).

With early alerts to problems, action would be taken to avoid higher-level alerts; if a higher-level alert should arise, more drastic remedial action would be invoked.

The actions taken at each level of alert are given below:

- Mid-level alert = Conference call between study investigators to discuss approaches to minimize further losses to follow-up/dropouts.
- High-level alert = Conference call between investigators and safety officer to determine further alterations of study protocol to complete the study with no further losses.
- Extreme-level alert = In the unlikely event of a 45% dropout rate occurs prior to the six-month measurement time point, study investigators, the safety officer, and the NIA program official would convene on a conference call to discuss the usefulness of continuing the study.

Additional Protocol Materials based on Supplemental Funding

Changes added with protocol amendment 5/22/2023

- 1. Add baseline(prior to/around hospital discharge) and longitudinal outcomes assessment (month 6, month 12) data collection timepoints
 - A. Cognition: Cognition will be measured by 4 objective tests of memory, attention, information processing speed, and executive cognitive function (Auditory Verbal Learning Test [AVLT], Digit Span, and Symbol Digit Modalities Test [SDMT], and Controlled Oral Word Association test [COWA]) using a telephone-based administration format, the Indiana University Telephone-Based Assessment of Neuropsychological Status (IU-TBANS) prior to/around hospital discharge, at 3-months post hospital discharge, 6 months post-hospital discharge.

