Previous research has demonstrated that these tests can be delivered reliably and precisely **in** person or by telephone.⁸⁴

- B. Depression and Anxiety: Research staff will collect PHQ-9 and GAD-7 over the phone or in person prior to/around hospital discharge, at 3 months post-hospital discharge, 6 months post-hospital discharge and 12 months post-hospital discharge.
- 2. Add Blood Sample Collection Time points (month 3, month 6, month 12).

During hospitalization we will collect blood samples prior to first intervention session (up to 10ml in tubes containing anticoagulant), at day 3, and at the end of the intervention period (up to 10 ml in tubes containing anticoagulant). Samples will also be collected at the month 3, month 6 and month 12 post hospital discharge visits (up to 10ml in tubes containing anticoagulant) in the clinic. This will be a total of up to 4 tablespoons of blood collected. The samples will be transported to the CTSI lab, and will be prepared and stored using deidentified labels.

3. Exploratory Aims added (1,2):

Exploratory Aim 1: Test the efficacy of the DDM treatment in slowing the rate of post-ICU cognitive decline in mechanically ventilated patients as compared to attention control. Hypothesis 1a: Patients in the DDM intervention group will have slower cognitive decline compared to the attention control group as measured by the IU-TBANS completed at 6- and 12-months after hospital discharge. Hypothesis 1b: This difference in cognitive trajectories between the DDM intervention group versus the attention control group will be due, in part, to the DDM treatment decreasing the duration and severity of ICU delirium during the index ICU stay.

[figure not shown]

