Exploratory Aim 2: Determine whether the DDM treatment is associated with slower progression of ADRD pathology in older adult ICU survivors as compared to attention control. Hypothesis 2a: Patients in the DDM treatment group will have slower progression in measures of neurodegeneration (lower level of neurofilament light (NfL), phosphorylated tau-181 (p-tau 181), glial fibrillary acidic protein (GFAP), and S100B), AD pathology (higher levels of Aβ42/Aβ40), vascular pathology (lower levels of C-reactive protein (CRP))⁸ and inflammation (lower levels of interleukins (IL)-1, 6, and 8) as measured by blood-based biomarkers collected in the ICU and 3, 6 and 12 months after hospital discharge, compared to those in the attention control group. Hypothesis 2b: These differences in progression of ADRD pathology between the DDM treatment versus control group will be due, in part, to the DDM treatment decreasing the duration and severity of ICU delirium during the index ICU stay.

4. Exploratory Aims Statistical Considerations added (1,2)

Exploratory Aim 1: Mixed effects models will be used with repeated IUTBANS scores (collected at baseline, 6 months and 12 months as the outcome measures), group, time, and a group and time interaction as independent variables while adjusting for stratification variables and other potential baseline covariates found to be significantly different in univariate comparisons. A significant interaction between group and time would indicate differences in changes of cognitive functions over time between the two groups.

Exploratory Aim 2: Changes in the biomarkers will be calculated and used as the dependent variables in ANCOVA models with group as the independent variable and adjusting for stratification variables and baseline covariates that are found to be different among the groups in univariate comparisons. Mixed effects models will be used to explore the association between oxidative stress biomarkers at ICU admission and those collected at 3, 6-, and 12- months post discharge.

5. Revised Figure 3: DDM Trial Flow Chart

6. Revised Table Time-line of Data Collection and Outcomes Assessments

			ata Collection a					
Co	Method of Collection	ne-line of Data Collection and Outcome ICU Phase			Hospital Discharge	Post Hospital Discharge		
		Enrollment	Intervention Phase	Post- intervention phase		3 months	6 months	12 months
Demographics (Age, race, gender, education, Insurance)	EMR	Х						
Clinical Data (lab	EMR	Х						

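### PHQ-9 and GAD-7 are now scheduled at four visits but have a specified analysis at only one; a repeated-measures model would define the rest and use partial records (minor)

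*Combined protocol and SAP*

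**What the plan says.** Secondary Specific Aim 2 states the mood hypothesis at one time point: "lower depression and anxiety scores on the Patient Health Questionnaire (PHQ-9) and Generalized Anxiety Disorder (GAD-7) scales at 3 months post hospital discharge". Item b of Statistical Considerations matches it: "ANCOVA models will be used to compare IU-TBANS, PHQ-9, and GAD-7 collected at three months post hospital discharge". The model has a group term and adjusts for baseline covariates that are not named.

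The section Additional Protocol Materials based on Supplemental Funding then widens collection. Its item 1 reads "Add baseline(prior to/around hospital discharge) and longitudinal outcomes assessment (month 6, month 12) data collection timepoints", and item 1.B has staff "collect PHQ-9 and GAD-7 over the phone or in person prior to/around hospital discharge, at 3 months post-hospital discharge, 6 months post-hospital discharge", and again at 12 months. The revised time-line table marks the mood scales at all four visits. Item 4, which adds the statistics for the new exploratory aims, gives a longitudinal model for cognition only: "Mixed effects models will be used with repeated IUTBANS scores (collected at baseline, 6 months and 12 months as the outcome measures". Exploratory Aim 2 concerns blood biomarkers. Neither the added aims nor their statistics mention PHQ-9 or GAD-7.

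**The concern.** Three rounds of mood data will be gathered with no stated hypothesis, model or summary. How to analyse 6 and 12 months would then be decided after the data are in hand.

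The single-visit ANCOVA also leaves out any living patient without a 3-month score, even one with scores at discharge or later. Telephone follow-up of ICU survivors is where such gaps are likely. The plan already uses mixed models for repeated in-ICU scores and for later cognition, but not for mood.

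The amendment calls the discharge visit a baseline, although it falls after randomization and usually after the intervention. Read with the unnamed baseline covariates of item b, that label leaves room to adjust the mood comparison for a score that treatment may already have changed.

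**Working it through.** **1. Visits against analyses.**

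| Mood visit | Scheduled | Hypothesis | Analysis |
|---|---|---|---|
| Around discharge | yes (amendment) | none | none |
| 3 months | yes | Secondary Aim 2 | ANCOVA |
| 6 months | yes (amendment) | none | none |
| 12 months | yes (amendment) | none | none |

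**2. The plan's own figure.** The power paragraph gives 80% power at 0.5 SD for the 3-month outcomes (labelled Aim 3 there). It does not restate N, so I take 128 from the sample-size paragraph, that is 64 per arm at 1:1. Two-sided testing is assumed. Noncentrality is 0.5 × √(64/2) = 2.83 on 126 degrees of freedom, so power is 80.1%. The figure reproduces.

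**3. What the other visits can add at 3 months.** Take unit SD, n per arm, and a share m without the 3-month score. Let R² be the squared multiple correlation of the 3-month score with the other mood scores. Means are free in each arm at each visit, because the discharge score follows randomization. The covariance is treated as known.

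- 3-month scores only: variance = 2 / [n(1 − m)].
- Repeated measures, if all who miss the call have the other scores: variance = (2/n) × [(1 − R²)/(1 − m) + R²].
- Ratio = 1 − mR².

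At m = 0 the ratio is 1.000 whatever the correlation, so there is no gain. With equal correlation ρ and three other visits, R² = 3ρ²/(1 + 2ρ), which is 0.375 at ρ = 0.5 and 0.6125 at ρ = 0.7. At m = 0.2 the ratios are 1 − 0.2 × 0.375 = 0.925 and 1 − 0.2 × 0.6125 = 0.878. These are best cases.

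**4. Partial recovery.** Assumed, since the documents give no figures: ρ of 0.5-0.7; 20-30% of survivors miss the call; of those, 50-80% have a discharge score and 16-40% a later one. For the discharge score alone, with share f recovered, m′ = mf/(1 − m + mf) and the ratio is 1 − m′ρ².

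- Low end: m′ = 0.10/0.90 = 0.111; ratio 1 − 0.111 × 0.25 = 0.972; gain 1/0.972 − 1 = 2.9%.
- High end: m′ = 0.24/0.94 = 0.255; ratio 1 − 0.255 × 0.49 = 0.875; gain 1/0.875 − 1 = 14.3%.

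Adding the later scores by generalized least squares gives 3.5% to 17.0% with equal correlations, so about 3-17%. Other correlation patterns move the upper end by a point or two.

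**5. Patients followed before the amendment.** They supply only a 3-month score, so the gain scales with the share who have the added visits (same missed-call rate assumed). If half do, 3.5% and 17.0% become 1.7% and 8.5%, or about 2-9% across the correlation patterns.

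**6. The discharge score as a covariate.** If the effect were 0.5 SD at both visits, the adjusted effect would be 0.5(1 − ρ) and the residual SD √(1 − ρ²). At ρ = 0.3 this is 0.35 over 0.954, with 54% power at 64 per arm. At ρ = 0.8 it is 0.10 over 0.60, with 16% power.

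**The case against.** A 3-month ANCOVA is a valid analysis of a 3-month hypothesis, and with complete data the other visits add nothing to it. The added visits came with funding for cognition and biomarker aims. Item c (Missing Data) is not silent: it compares patients with and without the 3-month assessment and adjusts for variables associated with missingness. It also promises sensitivity analyses, though that sentence follows the day-7 outcome. The change would also treat mood differently from IU-TBANS, which shares the sentence in item b.

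Most of this stands and limits the size of the point. It does not close the gap: item c does not use the other mood scores, and IU-TBANS has a longitudinal model under Exploratory Aim 1 while mood has none.

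Stronger readings that a reader might infer are not supported:

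- **The extra scores will be discarded.** No text says so; no analysis is specified for them.
- **Precision at 3 months is lost in general.** The ratio of 1.000 with complete data rules this out.
- **Power recovers from 74.6% (56 per arm) to 78-79%.** That needs a 10% gain. Going from 128 to 112 is a 12.5% loss, where the same assumptions give about 2-6%. Reading 112 as 30% lost from 160 brings in patients who died in hospital and have no other score to use.
- **The ANCOVA is materially biased.** Simulated missingness driven by discharge mood shifted the contrast by about 0.02 SD, against a standard error of √(2/56) = 0.19 SD, and the mechanism is itself assumed.

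**Conclusion.** The point holds as a minor one. Three of four scheduled mood rounds have no specified analysis, and the one analysis that exists cannot use a survivor who missed the 3-month call. This rests on the text alone.

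The precision gain is a secondary benefit and is conditional: none with complete 3-month data, about 3-17% in effective sample size if all patients have the added visits, and about 2-9% if half do. The correlations, missed-call rate, recovery rates and share followed under the amendment are all assumptions. Neither a quoted power improvement nor bias is a reason for the change.

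The plan does not say that the discharge score will be a covariate. It leaves that open, and one sentence would close it.

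**What to change.** For PHQ-9 and for GAD-7, replace the 3-month ANCOVA in item b with one mixed model for repeated measures:

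- **Outcomes:** discharge, 3-, 6- and 12-month scores.
- **Terms:** group, visit (categorical), group-by-visit, hospital and the planned baseline covariates, with unstructured covariance.
- **Inference:** the 3-month group contrast remains the secondary test; the 6- and 12-month contrasts are labelled exploratory.
- **Discharge score:** entered as an outcome, never as a covariate, because it is taken after randomization despite the baseline label.
- **Deaths:** state that the 3-month contrast refers to patients alive at 3 months, so that scores are not implicitly extrapolated past death.

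The cost is wording in the analysis plan. The data are already scheduled, the hypothesis is unchanged, and patients from before the amendment still contribute their 3-month score. The downsides are a model with more parameters and reliance on missing at random.
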